9.7.1.3 Analysis Strategy

Primary analysis will be primarily based on the PP population and analysis, based on mITT population with missing value imputation for primary endpoint will be considered as supportive analyses.

The primary efficacy endpoint in this study is the change in hepatic fat content from baseline following 24 weeks of treatment measured by MRI-PDFF. The change from baseline of hepatic fat will be determined as (Visit 8 [Week 24] value – Baseline value).

The actual values observed and change from baseline values of hepatic fat content will be summarized using the number of non-missing observations (n), mean (Mean), standard deviation (SD), median, minimum (Min) and maximum (Max) by treatment groups for baseline and scheduled all visits (i.e. baseline to Week 24 visits).

To check the mean significance difference between baseline and scheduled visit for Week 24, a paired t-test at 5% level of significance will be used.

Following sample SAS code will be used for paired t-test:

```
proc ttest data=data sides=2 alpha=0.5;
paired BASE*AVAL;
run;
```

Where AVAL: variable with post baseline value; BASE: variable with baseline value.

Document Title:	Statistical Analysis Plan		
Version Number:	Final 1.0	Date:	18Oct2024
Protocol Number:	SARO.17.009	Sponsor Name:	Zydus Therapeutics INC

The primary efficacy endpoint, the change from baseline in hepatic fat content at Week 24 will be analyzed using an analysis of covariance (ANCOVA) model. The model will include change in the hepatic fat content values from baseline as dependent variable, treatment group as a fixed effect and baseline values as a covariate.

The estimate the LS means for treatment groups and its 95% confidence interval, the difference of LS Mean for treatment group (Saroglitzaz magnesium 4 mg – Placebo) and its 95% confidence interval of the difference of LS Mean for treatment group, and p-value to check the significance difference at 5% level of significance will be generated using ANCOVA model.

The following sample SAS code pertains to the ANCOVA analysis:

```
proc mixed data=DATA;
class TRT;
model CHG = BASE TRT/solution;
lsmeans TRT/ stderr pdiff cl alpha=0.05;
ods output diffs = DIFFS lsmeans = LSMEANS;
run;
```

Where, CHG: variable with change from baseline values; BASE: variable with baseline values; TRT: variable with treatment values.

The effectiveness of the investigational product (Saroglitzaz Magnesium 4 mg) compared to placebo will be obtained and thus the null and alternative hypothesis will be state as follows:

Null hypothesis, $H_0: S \leq P$

i.e., Mean change in hepatic fat content for treatment group (Saroglitzaz magnesium 4 mg) – Mean change in hepatic fat content for control group (Placebo) ≤ 0

Alternative hypothesis, $H_1: S > P$

i.e., Mean change in hepatic fat content for treatment group (Saroglitzaz magnesium 4 mg) – Mean change in hepatic fat content for control group (Placebo) > 0

Where, S = Treatment effect of Saroglitzaz Magnesium 4 mg, P = Treatment effect of Placebo.

The effectiveness of the investigational product (Saroglitzaz magnesium 4 mg) will be achieved using the lower bound of the 95% confidence interval of the LS Mean difference between the treatment groups. If the lower bound of the 95% confidence interval of the LS Mean difference between the treatment groups is greater than 0, Investigational product (Saroglitzaz magnesium 4 mg) will lead to the conclusion that the treatment effect of Saroglitzaz Magnesium 4 mg is statistically significantly greater than the treatment effect of placebo group and hence the test drug is more effective than placebo, and the study will be considered a success.

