8.1 Descriptive Statistics

The following descriptive statistics will be calculated for continuous data as well as for categorical data:

The summary statistics will be displayed with the following digits:

Description	Characteristic	Number of Decimal Places
Number of non-missing participants/observations	n	0
Number of events	E	0
Count corresponding to the number of participants for a group	N	0
Percentage [#]	%	1 decimal
Number of missing observations*	Missing	0
Mean	Mean	As in source + 1
Adjusted Least Square Mean	LS Mean	As in source +1
Standard Deviation	SD	As in source + 2
Standard Error	SE	As in source + 2
Minimum	Min	As in source
Median	Median	As in source + 1
Maximum	Max	As in source
Probability value	p-value	4 decimals
Confidence Interval	CI	2 decimals
Change From Baseline values	CFB	As in source
Percent Change from Baseline	PCB	2 decimals

*: If no observation is missing then “nmiss” row will not be printed.

#: Number of decimal places can be more than one, if necessary. All table percentages should be rounded to one decimal place if not stated otherwise.

Data will be summarized by the treatment groups (i.e. Saroglitazar Magnesium 4 mg or Placebo) wherever appropriate. The total number of participants in the treatment groups (N) under the stated population will be displayed in the header of summary tables as required.

Data will be summarized using descriptive statistics for continuous variables. Unless otherwise stated, descriptive statistics will include total number of participants with non-missing value of a variable/parameter (n), mean (Mean), Standard Deviation (SD), minimum (Min), median (Median), and maximum (Max).

In case of n=1, (where ‘n’ indicates the number of evaluable participants at the particular time point) then “SD” will be presented as ‘NE’ i.e. ‘Not Evaluable’.

In case of n<1, (where ‘n’ indicates the number of evaluable participants at the particular time point) then “Mean, SD, Median, Minimum, Maximum” will be presented as ‘NE’ i.e. ‘Not Evaluable’.

Document Title:	Statistical Analysis Plan		
Version Number:	Final 1.0	Date:	18Oct2024
Protocol Number:	SARO.17.009	Sponsor Name:	Zydus Therapeutics INC

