9.7.1.4 Handling of Missing values

For the primary analysis, resulting missing values will be replaced using MI procedure (like a hypothetical strategy in the estimand framework). The data will be separated into two subsets based on the treatment groups which will ensure that the imputation process accounts for potential difference between these

Document Title:	Statistical Analysis Plan		
Version Number:	Final 1.0	Date:	18Oct2024
Protocol Number:	SARO.17.009	Sponsor Name:	Zydus Therapeutics INC

groups. Complete dataset will be generated using PROC MI and recombine the data set for subsequent analysis. The number of imputed data set should be sufficient to ensure reliable result. The number of imputations (m) may be determined using fraction of missing information and the percentage of missing data. Generally, 5 to 20 imputations are required to perform to ensure robust result. A productive mean approach or regression method can be used for the imputation. PROC MIANALYZE will be used to combine the results of complete dataset results.

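### The paired t-test code in SAP 9.7.1.3 sets alpha to 0.5, while the text sets a 5% level, so the printed confidence limits would be 50% limits

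*SAP*

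**What the plan says.** SAP 9.7.1.3 adds a before-after comparison to the primary endpoint analysis. For baseline against Week 24, "a paired t-test at 5% level of significance will be used". The code is introduced with "Following sample SAS code will be used for paired t-test", and its first line is "proc ttest data=data sides=2 alpha=0.5".

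The ANCOVA code later in the same section has "lsmeans TRT/ stderr pdiff cl alpha=0.05", which agrees with the 5% level and 95% intervals stated for that model.

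Three other places bear on the point:

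- The success rule in SAP 9.7.1.3 rests on the ANCOVA interval: "If the lower bound of the 95% confidence interval of the LS Mean difference between the treatment groups is greater than 0".
- On grouping, SAP 8.1 says "Data will be summarized by the treatment groups (i.e. Saroglitazar Magnesium 4 mg or Placebo) wherever appropriate", and the descriptive summaries of hepatic fat in 9.7.1.3 are to be given "by treatment groups for baseline and scheduled all visits". The sentence that specifies the paired test does not mention treatment group, and its code has no BY or CLASS statement.
- The table of differences from the protocol in SAP section 10 says nothing about the paired test or its level.

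**The concern.** The text and the code disagree by a factor of ten on the same quantity, a few lines apart. Although labelled a sample, the code is also described as what will be used, so a programmer who copies it would follow the SAP and still produce output that contradicts it.

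The output at risk is the confidence interval for the mean change in hepatic fat. If limits at the 50% level reached a table and were read as 95% limits, the change would look about three times as precise as it is. A reader who used those limits as the test would exclude zero half the time when there is no change, instead of 5% of the time.

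A second, smaller point concerns the missing BY statement. This is an ambiguity and not a contradiction. Run on a dataset that holds both arms, the code gives one before-after test across active and placebo together, which answers no question the trial poses.

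**Working it through.** **Inputs**

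- Level in the text: 0.05 (SAP 9.7.1.3).
- Alpha in the paired-test code: 0.5, with two sides requested (SAP 9.7.1.3).
- Alpha in the ANCOVA code: 0.05 (SAP 9.7.1.3).
- Recruitment closed at 60 (SAP 7.3 and 8.5); dropout rate 20% (SAP 8.5).
- Assumption: the 60 are split equally between the arms.

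**Step 1: does the code give the stated level?** Confidence level = 100 × (1 − alpha)%.

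- Text: 100 × (1 − 0.05) = 95%.
- ANCOVA code: 100 × (1 − 0.05) = 95%, which agrees with its text.
- Paired-test code: 100 × (1 − 0.5) = 50%, which does not.

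Sidedness does not explain the gap. The code asks explicitly for a two-sided test, and neither 0.05 nor the one-sided 0.025 equals 0.5.

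**Step 2: how much narrower are the limits?** The half-width of a paired interval is t(1 − alpha/2, n − 1) × s/√n. The factor s/√n cancels in the ratio, so

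ratio = t(0.75, n − 1) / t(0.975, n − 1).

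| Case | n | t(0.75) | t(0.975) | Ratio |
|---|---|---|---|---|
| Per arm, after 20% dropout (60 × 0.8 / 2) | 24 | 0.6853 | 2.0687 | 0.331 |
| Per arm, no dropout (60 / 2) | 30 | 0.6830 | 2.0452 | 0.334 |
| Both arms pooled, after dropout (60 × 0.8) | 48 | 0.6797 | 2.0117 | 0.338 |
| Both arms pooled, no dropout | 60 | 0.6787 | 2.0010 | 0.339 |

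The per-protocol set may be smaller than 24 per arm, because it also requires 80% to 120% compliance and no relevant deviation (SAP 8.2). At 20 per arm the ratio is 0.329, and at 15 it is 0.323. Every case comes to about one third.

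**Step 3: what does not change?** The test statistic is the mean difference divided by s/√n, and the two-sided p-value is 2 × (1 − F(|t|)), where F is the t distribution function with n − 1 degrees of freedom. Alpha enters neither. A p-value compared with 0.05 is therefore still a 5% test. The ANCOVA is a separate procedure with its own, correct, alpha.

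**The case against.** The strongest case against the point is that almost nothing follows from it. The SAP asks for a test at the 5% level, and the p-value that the code prints delivers exactly that. No interval is requested from this test. The comparison is a supplementary before-after check that does not appear in the protocol's primary analysis (Protocol 8.4.2.1), and the code is labelled a sample. All of this stands, and it is why the point is rated minor.

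A zero could also have been lost when the PDF was converted to text, since product names nearby are spelled inconsistently. This cannot be ruled out without looking at the PDF. Against it, the 0.05 in the ANCOVA code of the same section came through intact, and so did the rest of the code.

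On the BY statement, the objection is that by-arm testing is inferred. SAP 8.1 concerns summaries, and only where appropriate; the by-treatment phrase in 9.7.1.3 belongs to the descriptive statistics. That is fair. By-arm testing is the sensible reading, but the sponsor should confirm it.

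None of this reconciles 0.5 with 5%.

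**Conclusion.** The concern holds. SAP 9.7.1.3 contradicts itself on the level of the paired test, and the value in the code is very probably a slip for 0.05. Followed as written, the code prints 50% limits about one third as wide as the 95% limits that the text implies (0.331 to 0.334 per arm at the recruited size, assuming an equal split and dropout between 0 and 20%; slightly lower if the per-protocol set is smaller). No p-value, ANCOVA estimate, sample-size figure or success decision changes. The severity is minor. It is still worth correcting because the wrong number sits in code specified for the primary endpoint variable.

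**What to change.** Check the line against the SAP's PDF, then change the option in the PROC TTEST statement to `alpha=0.05`, so that it matches the text and the ANCOVA code.

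In the same edit, state whether the paired test is run within each arm. If it is, sort the data by `TRT` and add `by TRT;` to the PROC TTEST step.

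One further change is needed only if the paired test is also run on the imputed mITT data, which the SAP does not explicitly plan. In that case, sort and run by `TRT` and `_Imputation_`, then pool the mean differences and standard errors by arm, in line with SAP 9.7.1.4: "PROC MIANALYZE will be used to combine the results of complete dataset results".

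Optionally, reverse the pairing to `AVAL*BASE`, so that the printed difference has the sign of Week 24 minus baseline, as the SAP defines change. The present order is not an error.

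The cost is one digit, plus a sort step and a BY line. Data, sample size, the primary analysis and timelines are unaffected.

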8.3 Definitions

In the following table, the required definitions and calculation for derivation during the analysis are summarized.

Document Title:	Statistical Analysis Plan		
Version Number:	Final 1.0	Date:	18Oct2024
Protocol Number:	SARO.17.009	Sponsor Name:	Zydus Therapeutics INC

Term	Definition / Way of Calculation
Baseline	Baseline is defined as the last non-missing observation (including scheduled and unscheduled assessments within the pre-treatment period) prior to the first dose administration of study drug.
Change from Baseline	Post Baseline Value - Baseline value.
Percentage Change From Baseline	$\frac{(\text{Post Baseline} - \text{Baseline})}{\text{Baseline}} \times 100$
Treatment Start Date/time	Date/time of first dose administration in the study.
Treatment End Date/time	Date/time of last dose administration in the study.
Treatment Emergent Adverse Event (TEAE)	Treatment-emergent AEs are defined as any AE that started after the first dose of study drug or started before the first dose but increased in severity or frequency after administration of the initial dose of study drug.
Duration of Treatment (Days)	Treatment End Date – Treatment Start Date + 1.
Duration of Study (Days)	Last Visit Date – Informed Consent Date + 1.

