8.5 Sample Size Calculation

The primary efficacy endpoint of this study is "change from baseline in hepatic fat content at Week 24 as measured by MRI-PDFF".

Sample Size at the Study Initiation:

The sample size was estimated assuming change of 0.8 unit from baseline (treatment difference), standard deviations of 0.3 and 0.4 units, at one-sided 2.5% level of significance (α) and with β level of 0.20 (i.e., 80% power). Using these assumptions, at least 23 completed subjects in each arm (Saroglitazar Magnesium 4 mg and placebo) was required for PP analysis. Considering ~20% dropout rate, around 60 subjects should be enrolled in this proof-of-concept study, with 1:1 treatment allocation ratio i.e. Saroglitazar Magnesium 4 mg (30): placebo (30).

There was no available data with this type of study. In order to understand the disease prevalence and enhance our knowledge of correlation of PCOS and NAFLD, determination of sample size section has been revised.

Revised Sample Size based on current protocol version 5.0:

A sample size of 74 completed participants (37 participants in each treatment arm) will provide 80% power to detect a 4% treatment difference in change from baseline in hepatic fat content at Week 24 between Saroglitazar 4 mg and Placebo using a two-sided 5% level of significance based on a two-sample t-test, assuming change from baseline in hepatic fat content of 9% at Week 24 in Saroglitazar 4 mg treatment arm with a common standard deviation of 0.6.

Document Title:	Statistical Analysis Plan		
Version Number:	Final 1.0	Date:	18Oct2024
Protocol Number:	SARO.17.009	Sponsor Name:	Zydus Therapeutics INC

Assuming a 20% dropout rate at week 24, approximately 90 participants will be randomized in a 1:1 ratio to receive either Saroglitzazar 4 mg (45 Participants) or placebo (45 Participants). The sample size estimation was performed using PASS 14 software.

A total of 12 Participants, 6 Participants in each treatment arm will be included in the pharmacokinetic assessment.

In view of the difficulty and challenges observed in recruitment of study population, it was decided to close recruitment at 60 participants.

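### The sample code for the paired t-test in SAP 9.7.1.3 does not match the SAP text: it reverses the sign of the change, has no treatment statement, and sets 50% confidence limits (minor)

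*SAP*

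**What the plan says.** SAP section 9.7.1.3 fixes the direction of the primary variable: "The change from baseline of hepatic fat will be determined as (Visit 8 [Week 24] value – Baseline value". The definitions table in SAP 8.3 gives the same rule for every variable: "Post Baseline Value - Baseline value". On this scale a fall in liver fat is negative.

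Section 9.7.1.3 then adds a paired t-test at the 5% level comparing baseline with Week 24. The sentence announcing it names no treatment arm. It is followed by "Following sample SAS code will be used for paired t-test" and a three-line program. The procedure line is "proc ttest data=data sides=2 alpha=0.5", the analysis line is "paired BASE*AVAL", and the key reads "Where AVAL: variable with post baseline value; BASE: variable with baseline value". There is no BY, CLASS or WHERE statement.

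Two nearby texts do refer to arms. The descriptive summaries in the preceding paragraph of 9.7.1.3 are by treatment group, and SAP 8.1 says data are summarised by treatment group where appropriate. The ANCOVA code later in 9.7.1.3 includes the treatment variable. The success rule uses only the ANCOVA difference in LS means.

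**The concern.** PROC TTEST takes the first variable minus the second, so the printed code estimates baseline minus Week 24. Its mean and confidence limits would have the opposite sign to the change summaries and to the ANCOVA's dependent variable. Section 9.7.1.3 also states its success rule as a value above zero, so a positive number in the paired output is easy to misread as the favourable result.

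Without a treatment statement, the program run as printed tests all women together. Such a test asks whether liver fat changed in the trial as a whole. It cannot separate drug from placebo, yet it stands ahead of the ANCOVA in the primary analysis strategy.

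With `alpha=0.5` the printed limits would be 50% limits, although the text sets a 5% level.

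At stake is a misleading supporting output on the primary endpoint. The primary inference is not affected.

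**Working it through.** **1. Sign.** The SAP's change is AVAL − BASE. The code gives BASE − AVAL = −(change). If the planned figures are read as percentage-point falls of 9 on drug and 9 − 4 = 5 on placebo, in equal arms, the combined paired mean prints as (9 + 5)/2 = +7, while the SAP's change is −7 and the ANCOVA difference is about −4. Swapping the order changes t to −t and leaves the two-sided p-value alone. In one simulated dataset of 48, t = +6.86 became −6.86, with p = 1.3 × 10⁻⁸ both ways.

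**2. SD for the size of the pooling effect.** The plan's own figure is 37 completers per arm for 80% power, difference 4%, SD 0.6, two-sided 5% two-sample t-test (SAP 8.5).
- Difference 4 and SD 0.6 in the same units: 2 per arm. The stated figure is not reproduced.
- Difference 4 and SD 6: 37 per arm, power 80.8%. Reproduced.
- SD giving exactly 80% at 37 per arm: 6.06.

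I therefore assume an SD of change of 6.06 points. This is not a figure in the documents.

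**3. Completers.** Recruitment closed at 60 (SAP 8.5). With the planned 20% dropout, 60 × 0.8 = 48, or 24 per arm. This is also an assumption.

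**4. Chance of p < 0.05 when the drug does nothing.** If both arms fall by m points, the paired t statistic on n women has noncentrality δ = m/(6.06/√n). The rejection probability is P(|T| > t₀.₉₇₅) with n − 1 degrees of freedom. For n = 48, 6.06/√48 = 0.875.

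| Common fall m (points) | δ | Chance, both arms combined |
|---|---|---|
| 0 | 0 | 5% |
| 1 | 1.14 | 20% |
| 2 | 2.29 | 61% |
| 3 | 3.43 | 92% |
| 5 | 5.72 | >99.9% |

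The 5-point row is the placebo change inferred from the sizing text, "assuming change from baseline in hepatic fat content of 9% at Week 24 in Saroglitazar 4 mg treatment arm", less the 4% difference. With SD 6 the 2-point row becomes 62% and the other rounded entries do not change.

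**5. Splitting by arm.** With 24 women in one arm the chance is 34% at a 2-point fall and 97% at 5 points. A by-arm run removes the pooling, but each test still responds to a fall common to both arms.

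**6. ANCOVA for comparison.** In simulations with no drug effect (common falls of 0, 2 and 5 points; 48, 60 and 74 completers; SD of change 6; assumed baseline mean 18 and SD 6; 4,000 runs each), the treatment contrast was significant in 4.5% to 5.4% of runs.

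**7. Confidence limits.** At 47 degrees of freedom, t₀.₇₅ = 0.680 and t₀.₉₇₅ = 2.012. The 50% half-width is 0.680/2.012 = 34% of the 95% half-width. Within one arm (23 degrees of freedom) it is 0.685/2.069 = 33%.

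**The case against.** The code is labelled as a sample. The ANCOVA sample also omits the population selection and subgroup split that the text requires, so these snippets may be templates. With by-arm summaries in the preceding paragraph and in SAP 8.1, a by-arm test may well be intended. This stands in part: a reader might infer that the SAP has decided to pool the arms, and no text says so. Equally, no text says that the paired test is run by arm, and the SAP states that this code will be used, so the omission needs filling.

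The test is two-sided, so the reversed sign cannot change its p-value. The SAP does not say that the mean or limits from this procedure will be tabulated. Both points are correct, and they confine the harm to the estimate and limits, if these are reported.

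The paired test decides nothing and is presented only as baseline versus Week 24. This is also correct, and it is the main reason for the low grade.

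A reader might go further and infer that the test will be significant even if the drug does nothing. The documents do not support this without a condition: with no common fall it rejects at 5%. A fall in both arms is plausible. Entry requires a fat fraction of at least 10%, and the screening scan serves as baseline, so regression to the mean could lower both arms. The documents do not quantify that effect. The 5-point placebo figure is itself an inference, because the SAP does not state the direction of the 4% difference or whether the percentages are absolute or relative.

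**Conclusion.** The mismatch holds and is minor. Run as printed, the code reports the opposite sign to the SAP's defined change, tests both arms together, and prints limits about one third as wide as 95% limits. It changes neither the ANCOVA nor the success rule, and the sign does not affect the two-sided p-value.

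The supportable statement on significance is conditional: the combined test can be significant without any drug effect if both arms fall. The chance runs from 5% with no common fall to over 99.9% at 5 points. These figures rest on an SD of change near 6 points, 48 completers, and percentages read as absolute points.

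The direction of the ANCOVA success rule in 9.7.1.3 is a separate matter, and correcting the paired test does not settle it.

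**What to change.** In the paired t-test code of SAP 9.7.1.3:
- replace the pair with `paired AVAL*BASE;`, so that the output is Week 24 minus baseline;
- add `by TRT;`, on data sorted by treatment;
- change `alpha=0.5` to `alpha=0.05`, so that the limits are 95% and match the stated 5% level. Without this, the corrected code would still print 50% limits.

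Add one sentence stating that the paired test is run within each arm, is descriptive, and is not evidence of drug versus placebo. Dropping the within-arm p-value, or deleting the test because the ANCOVA LS means already give within-arm changes, is an option and a matter of preference.

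The cost is three small code edits and one sentence. No new data are needed and the primary model does not change.

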8.3 NULL AND ALTERNATIVE HYPOTHESIS

Below is the hypothesis of primary efficacy endpoint:

Null hypothesis: $H_0: S \leq P$

Alternative hypothesis $H_1: S > P$

Where: S = Treatment effect of Saroglitazar Magnesium 4 mg, P = Treatment effect of Placebo

Rejection of the null hypothesis will lead to the conclusion that the treatment effect of Saroglitazar Magnesium 4 mg is statistically significantly greater than the treatment effect of placebo group and hence the test drug is more effective than placebo.

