8.4.2.1 Primary Efficacy Analysis

The primary analysis for the primary efficacy endpoint will be based on PP population. The primary efficacy endpoint in this study is the change in hepatic fat content from baseline following 24 weeks of treatment as measured by MRI-PDFF. The change from baseline of hepatic fat will be determined as (Week 24 value – Baseline value).

The primary endpoint will be summarized and change from baseline to Week 24 will be evaluated using ANCOVA model with treatment as factor and baseline value as covariate. Statistical significance will be tested at a one-sided p-value <0.025 .

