9.7.1.2 Estimand

The attributes for the primary estimand related to the first primary endpoint are described below:

1. Treatment: The study compares the efficacy of the Investigational Product (i.e., Saroglitazar Magnesium 4mg) versus the Placebo as randomized in 1:1 ratio.
2. Population: The target population is female participants of PCOS with NAFLD, 18 to 45 years of age. Primarily, analysis will be based on the PP population.
3. Variable: The primary endpoint is the “Change in hepatic fat content from baseline to Week 24” measured by MRI-PDFF.
4. Intercurrent Events:

Document Title:	Statistical Analysis Plan		
Version Number:	Final 1.0	Date:	18Oct2024
Protocol Number:	SARO.17.009	Sponsor Name:	Zydus Therapeutics INC

- Missing Data: Participants may discontinue the study treatment before completing the Visit 8 (Week 24) period, might miss the Week 24 MRI-PDFF measurement, will be considered as missing. The missing data values may be imputed for primary endpoint analysis to consider the analysis treatment effect assuming all participants completed treatment as planned.
- Rescue/Concomitant medication: Participants might require additional treatments (rescue medication or concomitant medications) during the treatment period. The effect of the study treatment will be evaluated regardless of the rescue or concomitant medication.
- Change in ALT inclusion criteria: Participants recruited before the amendment may not fulfill the ALT inclusion criteria due to absence of inclusion criterion. A selection bias will be handled by conducting sensitive analysis, for analyzing subgroup treatment difference (within stratum) based on the ALT score, which will lead to assess whether the change in inclusion criteria has influenced the treatment effect. OR adjustment of the covariates for ALT levels can be performed.

5. Population Level Summary:

The primary efficacy endpoint, the change from baseline in hepatic fat content at Visit 8 (Week 24) will be analyzed using an analysis of covariance (ANCOVA) model. The effectiveness of the investigational product (Saroglitzazar magnesium 4 mg) will be achieved using the lower bound of the 95% confidence interval of the LS Mean difference between the treatment groups.

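### The SAP's success rule points the wrong way: as written, the trial succeeds only if liver fat changes less favourably on saroglitazar than on placebo

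*SAP*

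**What the plan says.** SAP 9.7.1.3 (Analysis Strategy) fixes each element of the primary decision:

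- **Variable.** "The change from baseline of hepatic fat will be determined as (Visit 8 [Week 24] value – Baseline value". Protocol 8.4.2.1 has the same definition: "The change from baseline of hepatic fat will be determined as (Week 24 value – Baseline value". The general definition in SAP 8.3 is also post-baseline minus baseline.
- **Contrast.** The quantity estimated from the ANCOVA is "the difference of LS Mean for treatment group (Saroglitzaz magnesium 4 mg – Placebo".
- **Alternative hypothesis.** The SAP explains S > P as the mean change on saroglitazar minus "Mean change in hepatic fat content for control group (Placebo) > 0".
- **Decision.** "If the lower bound of the 95% confidence interval of the LS Mean difference between the treatment groups is greater than 0", the conclusion is that the treatment effect exceeds placebo's, "hence the test drug is more effective than placebo, and the study will be considered a success".

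The lower-bound criterion recurs, without a threshold, in SAP 9.7.1.2 item 5, where effectiveness "will be achieved using the lower bound of the 95% confidence interval of the LS Mean difference between the treatment groups". It also appears in the SAP Section 10 table, as the replacement for the protocol's one-sided test at 0.025.

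**The concern.** The trial treats NAFLD and admits only women with a hepatic fat fraction of at least 10%, so the hoped-for result is a larger fall in liver fat on saroglitazar. With change defined as Week 24 minus baseline, a fall is negative, and a larger fall on saroglitazar makes saroglitazar minus placebo negative. A rule that needs the lower confidence bound above zero therefore looks for the opposite result.

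Two things are at stake. Applied literally, the pre-specified primary criterion calls an effective drug a failure and a harmful one a success. If the analysts instead reverse the rule once results are known, the primary criterion has been changed after unblinding. However obvious the intent, that is an avoidable weakness in the one confirmatory statement the trial makes.

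**Working it through.** **Step 1: sign of the rule.** Write C = Week 24 − baseline and D = mean C on saroglitazar − mean C on placebo.

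- Less liver fat is the benefit, so benefit means D < 0.
- The SAP's H1 is D > 0.
- The SAP's success condition is lower 95% bound of D > 0, which implies an estimated D > 0.

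The SAP's success region therefore lies wholly on the harm side. It does not require an absolute rise on saroglitazar; a significantly smaller fall than on placebo is enough.

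**Step 2: a bound that needs no assumptions about size.** At D = 0 the rule succeeds with probability 0.025, the upper tail of a two-sided 95% interval. That probability decreases as D becomes more negative. So for any true benefit, any SD and any sample size, the written rule succeeds less than 2.5% of the time.

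**Step 3: the plan's own sample size, to choose an SD for illustration.** SAP 8.5 and Protocol 8.6 state 37 completers per arm for 80% power, two-sided 5%, a 4% difference and an SD of 0.6. The normal approximation is n = 2(1.960 + 0.842)² × (SD/difference)².

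- Difference 4, SD 0.6: 2 × 7.849 × 0.0225 = 0.35, so 1 per arm.
- Difference 0.04, SD 0.6: 2 × 7.849 × 225 = 3,532 per arm.
- Difference 4, SD 6 (or 0.4 and 0.6): 2 × 7.849 × 2.25 = 35.3, so 36 per arm. The exact noncentral t gives 37 (power 80.8%, against 79.7% at 36).

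The printed inputs do not reproduce 37; a common scale with difference 4 and SD 6 does. SD 6 percentage points is therefore an assumption, used only in Step 4.

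**Step 4: probability of success under each rule.** The noncentrality is D / (6√(2/n)) with 2n − 2 degrees of freedom. For 24 per arm it is 4 / (6 × 0.2887) = 2.31; for 30, 2.58; for 37, 2.87. The sample sizes are the planned completers (37), all 60 participants at the closed recruitment (30), and 60 less 20% dropout (60 × 0.8 / 2 = 24).

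| n per arm | True D | Written rule: lower bound > 0 | Correct rule: upper bound < 0 |
|---|---|---|---|
| 37 | −4 (benefit) | 0.0000008 | 0.808 |
| 30 | −4 (benefit) | 0.000003 | 0.719 |
| 24 | −4 (benefit) | 0.000012 | 0.618 |
| any | 0 | 0.025 | 0.025 |
| 37 | +4 (harm) | 0.808 | 0.0000008 |
| 30 | +4 (harm) | 0.719 | 0.000003 |
| 24 | +4 (harm) | 0.618 | 0.000012 |

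These are two-sample t calculations. A simulation of the planned ANCOVA (20,000 trials, 37 per arm, SD 6) agrees. With a true benefit of 4 points the written rule succeeded in none of the trials and the correct rule in 80.1%; with a true harm of 4 points the written rule succeeded in 80.5%.

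**The case against.** The strongest defence is that S and P were meant as sizes of benefit. Protocol 8.3 says only "Where: S = Treatment effect of Saroglitazar Magnesium 4 mg, P = Treatment effect of Placebo", which allows that reading, and the SAP repeats those labels and speaks of the drug being more effective. The SAP is also not consistent about sign: its paired t-test code subtracts the Week 24 value from baseline, so a reduction is positive there, and the expected saroglitazar change of 9% is unsigned. This supports a drafting slip rather than a deliberate choice. It does not rescue the rule. The SAP goes on to equate S and P with mean change in hepatic fat, a quantity it has just defined as Week 24 minus baseline, and its Introduction and Section 10 say that the SAP governs where it differs from the protocol.

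A second defence is that the planned output also contains a p-value at the 5% level and the full interval, so a real benefit would be visible. That is true, but the p-value has no direction and success is tied to the lower bound.

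A third is that deviations from the SAP must be documented with reasons in the study report, so a correction could be made openly. That limits the damage; it does not make the rule right.

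One part of the opposing case changes the remedy. The sample `proc mixed` code uses a bare `pdiff`, so the sign of the reported difference depends on how the levels of TRT are ordered. With text labels sorted alphabetically it returns placebo minus saroglitazar, the reverse of the text. Correcting the wording alone could introduce a new sign error in execution.

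**Conclusion.** The concern holds: the primary success rule is wrong as written and must be fixed. The conclusion rests only on the SAP's own definitions of change and contrast and on lower liver fat being the benefit. Nothing elsewhere in either document corrects the direction. The guaranteed consequence is a success probability below 2.5% for any true benefit.

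The larger figures (0.62 to 0.81 for declaring success on a 4-point harm, and almost nil for a 4-point benefit) depend on the assumed SD of 6 points and on 24 to 37 completers per arm. They illustrate the size of the problem and are not needed to establish it.

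**What to change.** - **SAP 9.7.1.3.** State H0: mean change (saroglitazar) − mean change (placebo) ≥ 0 and H1: < 0. Declare success if the upper bound of the two-sided 95% CI for the LS-mean difference, saroglitazar − placebo, is below 0.
- **SAP 9.7.1.2 item 5 and the Section 10 table.** Replace the lower-bound wording with the same rule, including its threshold. Say that S > P in Protocol 8.3 is to be read as a greater reduction.
- **Sample code.** Fix the contrast instead of relying on level order, for example `pdiff=control('Placebo')` with the label matched to the actual coding of TRT. Check the sign on dummy data.

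An equivalent solution keeps the lower-bound rule and defines the contrast as placebo − saroglitazar throughout. Redefining change as baseline − Week 24 would also work, but it touches more text: SAP 8.3, SAP 9.7.1.3 and the protocol's definition.

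The cost is wording in three places and one line of code, with no new data and no effect on sample size. The documents do not show whether the database has been locked. If it has not, issue a dated SAP amendment before lock and unblinding. If it has, record the correction, its reason and its timing relative to unblinding in the study report.
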